6.3 Premature Termination or Suspension of Study or Investigational Site

6.3.1 Criteria for Premature Termination or Suspension of the Study

The study will be completed as planned unless 1 or more of the following criteria are satisfied that require temporary suspension or early termination of the study:

- New information or other evaluation regarding the safety or efficacy of the study drug that indicates a change in the known risk/benefit profile for TAK-831, such that the risk is no longer acceptable for subjects participating in the study.
- Significant violation of Good Clinical Practice (GCP) that compromises the ability to achieve the primary study objectives or compromises subject safety.
- Two or more subjects experience an SAE.*
- Two or more subjects experience alanine aminotransferase (ALT) and/or aspartate aminotransferase (AST) elevations >5 times the upper limit of normal (ULN) in the absence of a concomitant bilirubin increase.*
- One or more subjects experience ALT and/or AST elevations $>3 \times ULN$ in the presence of a total bilirubin increase $>2 \times ULN$ or an international normalized ratio (INR) >1.5 without findings of cholestasis or other alternate etiology to explain the elevations (ie, “Hy’s Law cases”).

- Two or more subjects experience ALT and/or AST elevations $>3\times$ ULN with the appearance of fatigue, nausea, vomiting, right upper quadrant pain or tenderness, fever, rash, and/or eosinophilia ($>5\%$).*

* Please note that the study may be terminated early prior to full attainment of these criteria (eg, if just 1 subject experiences 1 of these events) if warranted by safety data from the other subjects dosed in the study to date.

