7.5 Criteria for Discontinuation or Withdrawal of a Subject

The primary reason for discontinuation or withdrawal of the subject from the study or study drug should be recorded in the eCRF using the following categories. For screen failure subjects, refer to [Section 9.1.17](#).

1. Pretreatment event (PTE) or AE. The subject has experienced a PTE or AE that requires early termination because continued participation imposes an unacceptable risk to the subject's health or the subject is unwilling to continue because of the PTE or AE.

- Liver Function Test (LFT) Abnormalities

Study drug should be discontinued immediately with appropriate clinical follow-up (including repeat laboratory tests, until a subject's laboratory profile has returned to normal/baseline status, see [Section 9.1.8](#)), if the following circumstances occur at any time during study drug treatment:

- ALT or AST $>8 \times$ ULN, or
- ALT or AST $>5 \times$ ULN and persists for >2 weeks or based on clinical judgment of the investigator, or

- ALT or AST $>3\times$ ULN in conjunction with elevated total bilirubin $>2\times$ ULN or INR >1.5 , or
 - ALT or AST $>3\times$ ULN with appearance of fatigue, nausea, vomiting, right upper quadrant pain or tenderness, fever, rash, and/or eosinophilia ($>5\%$).
2. Significant protocol deviation. The discovery postrandomization that the subject failed to meet protocol entry criteria or did not adhere to protocol requirements, and continued participation poses an unacceptable risk to the subject's health.
 3. Lost to follow-up. The subject did not return to the clinic and attempts to contact the subject were unsuccessful. Attempts to contact the subject must be documented in the subject's source documentation.
 4. Voluntary withdrawal. The subject (or subject's legally acceptable representative) wishes to withdraw from the study. The reason for withdrawal, if provided, should be recorded in the eCRF.

Note: All attempts should be made to determine the underlying reason for the withdrawal and, where possible, the primary underlying reason should be recorded (ie, withdrawal because of an AE should not be recorded in the "voluntary withdrawal" category).

5. Study termination. The sponsor, IRB, or regulatory agency terminates the study.
6. Pregnancy. The subject is found to be pregnant.
Note: If the subject is found to be pregnant, the subject must be withdrawn immediately. The procedure is described in Section 9.1.10.

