If the ALT or AST remains elevated $>3\times$ ULN on these 2 consecutive occasions, the investigator must contact the Medical Monitor for consideration of additional testing, close monitoring, possible discontinuation of study drug, discussion of the relevant subject details and possible alternative etiologies. The abnormality should be recorded as an AE (please refer to Section 10.2.3 for reporting requirements related to abnormal LFT results).

The investigator or designee is responsible for transcribing or attaching laboratory results to the eCRF. The investigator will maintain a copy of the laboratory accreditation and the reference ranges for the laboratory used.

Laboratory reports must be signed and dated by the principal investigator indicating that the report has been reviewed and any abnormalities have been assessed for clinical significance. Any abnormalities identified prior to the first dose of study drug will require clear and complete documentation in the source documents as to the investigator's assessment of not clinically significant before proceeding with enrollment or randomization.

All clinically significant laboratory abnormalities must be recorded as a PTE/AE in the subject's source documents and on the appropriate eCRF. A clinically significant laboratory abnormality that has been verified by retesting will be followed until the abnormality returns to an acceptable level or a satisfactory explanation has been obtained.

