10.1.4 SAEs

An SAE is defined as any untoward medical occurrence that at any dose:

1. Results in DEATH.
2. Is LIFE THREATENING.
 - The term "life threatening" refers to an event in which the subject was at risk of death at the time of the event; it does not refer to an event that hypothetically might have caused death if it were more severe.
3. Requires inpatient HOSPITALIZATION or prolongation of existing hospitalization.
4. Results in persistent or significant DISABILITY/INCAPACITY.
5. Is a CONGENITAL ANOMALY/BIRTH DEFECT.
6. Is an IMPORTANT MEDICAL EVENT that satisfies any of the following:
 - May require intervention to prevent items 1 through 5 above.
 - May expose the subject to danger, even though the event is not immediately life threatening or fatal or does not result in hospitalization.
 - Includes any event or synonym described in the Takeda Medically Significant AE List ([Table 10.a](#)).

Table 10.a Takeda Medically Significant AE List

	Term
Acute respiratory failure/acute respiratory distress syndrome	Hepatic necrosis
Torsade de pointes/ventricular fibrillation/ventricular tachycardia	Acute liver failure Anaphylactic shock
Malignant hypertension	Acute renal failure
Convulsive seizure	Pulmonary hypertension
Agranulocytosis	Pulmonary fibrosis
Aplastic anemia	Confirmed or suspected endotoxin shock
Toxic epidermal necrolysis/Stevens-Johnson syndrome	Confirmed or suspected transmission of infectious agent by a medicinal product Neuroleptic malignant syndrome/malignant hyperthermia Spontaneous abortion/stillbirth and fetal death

Note: Terms identified on the Medically Significant AE List represent the broad medical concepts to be considered as “Important Medical Events” satisfying SAE reporting requirements.

PTEs that fulfill 1 or more of the serious criteria above are also to be considered SAEs and should be reported and followed up in the same manner (see Sections 10.2.2 and 10.3).

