10.2.3 Reporting of Abnormal LFTs

If a subject is noted to have ALT or AST elevated $>3 \times \text{ULN}$ on 2 consecutive occasions, the abnormality should be recorded as an AE. In addition, an LFT Increases page of the eCRF must be completed providing additional information on relevant recent history, risk factors, clinical signs and symptoms, and results of any additional diagnostic tests performed.

If a subject is noted to have ALT or AST $>3 \times \text{ULN}$ and total bilirubin $>2 \times \text{ULN}$ for which an alternative etiology has not been identified, the event should be recorded as an SAE and reported as per Section 10.2.2. The investigator must contact the Medical Monitor for discussion of the relevant subject details and possible alternative etiologies, such as acute viral hepatitis A or B or other acute liver disease or medical history/concurrent medical conditions. Follow-up laboratory tests as described in Section 9.1.8 must also be performed. In addition, an LFT Increases page of the eCRF must be completed and transmitted with the Takeda SAE form (as per Section 10.2.2).

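### The study-level liver stopping rules in Protocol 6.3.1 can count a milder ALT/AST case and skip the same case with raised bilirubin

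*Protocol*

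**What the plan says.** Protocol 6.3.1 introduces its list as criteria "that require temporary suspension or early termination of the study". Three of them are numeric transaminase rules:

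- **>5×ULN criterion (two or more subjects).** ALT and/or AST "elevations >5 times the upper limit of normal (ULN) in the absence of a concomitant bilirubin increase". It gives no bilirubin cut-off and does not mention etiology.
- **Hy's Law criterion (one or more subjects).** ALT and/or AST >3×ULN with total bilirubin >2×ULN "or an international normalized ratio (INR) >1.5 without findings of cholestasis or other alternate etiology to explain the elevations".
- **Symptom criterion (two or more subjects).** ALT and/or AST >3×ULN with a listed symptom or sign, or eosinophilia >5%. It has no bilirubin or etiology condition.

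An asterisk on the first and third allows earlier termination if the safety data warrant it. The section also has a general risk/benefit criterion and a criterion of two or more subjects with an SAE.

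Four other sections bear on the point:

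- Section 7.5 stops study drug for the individual at ALT or AST >3×ULN "in conjunction with elevated total bilirubin" >2×ULN or INR >1.5, with no etiology exception. It also stops at >8×ULN, or at >5×ULN that "persists for >2 weeks or based on clinical judgment of the investigator".
- Section 10.2.3 deals with ALT or AST >3×ULN plus bilirubin >2×ULN "for which an alternative etiology has not been identified, the event should be recorded as an SAE".
- Section 10.1.4 lets an event be judged an SAE if it "May expose the subject to danger, even though the event is not immediately life threatening or fatal".
- Section 9.1.8 says that if ALT or AST stays >3×ULN on two consecutive occasions "the investigator must contact the Medical Monitor for consideration of additional testing, close monitoring, possible discontinuation of study drug".

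**The concern.** The bilirubin condition in the >5×ULN criterion appears meant to pass cases with raised bilirubin to the stricter Hy's Law criterion, where one subject is enough. The hand-over is incomplete, because the receiving criterion filters on etiology and the sending one does not. A case can leave the first rule because bilirubin is raised, then fail the second because an explanation was found. Without a listed symptom or sign, it is not picked up by the third.

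The result is an inversion. Two symptom-free subjects with ALT 6×ULN, normal bilirubin and a cholestatic finding meet a criterion that requires a pause. Two with ALT 6×ULN, bilirubin 2.5×ULN and the same finding do not. At stake is whether dosing of the other subjects pauses by rule or only by judgment. Section 11.0 states that no data safety monitoring committee will be used, so the written rule carries more of that decision.

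**Working it through.** The plan gives no figure to reproduce here; the check is of logic. Each criterion is written as a condition on one subject, with ALT/AST fixed above 5×ULN:

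- >5×ULN criterion: true if there is no bilirubin increase.
- Hy's Law criterion: true if bilirubin >2×ULN or INR >1.5, subject to the etiology qualifier.
- Symptom criterion: true if a listed symptom or sign is present.

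**Patterns.** Bilirubin 0.8, 1.6 or 2.5×ULN; INR ≤1.5 or >1.5; other etiology no or yes; symptoms no or yes: 3 × 2 × 2 × 2 = 24.

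**Readings.** Two phrases are open. A bilirubin increase may mean >1×ULN or >2×ULN. The etiology qualifier may govern both limbs of the Hy's Law criterion or the INR limb alone. Both limbs is the natural reading, since the bullet is labelled as describing Hy's Law cases and Section 10.2.3 applies the same exclusion to the bilirubin combination. This gives four readings:

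- R1: >1×ULN, both limbs
- R2: >1×ULN, INR limb only
- R3: >2×ULN, both limbs
- R4: >2×ULN, INR limb only

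**Symptomatic patterns.** All 12 meet the symptom criterion under every reading.

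**Symptom-free patterns.** The other 12 are covered as follows:

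| Bilirubin (×ULN) | INR | Other etiology | Patterns | R1 | R2 | R3 | R4 |
|---|---|---|---|---|---|---|---|
| 0.8 | either | either | 4 | >5× | >5× | >5× | >5× |
| 1.6 | ≤1.5 | no | 1 | none | none | >5× | >5× |
| 1.6 | ≤1.5 | yes | 1 | none | none | >5× | >5× |
| 1.6 | >1.5 | no | 1 | Hy's | Hy's | both | both |
| 1.6 | >1.5 | yes | 1 | none | none | >5× | >5× |
| 2.5 | either | no | 2 | Hy's | Hy's | Hy's | Hy's |
| 2.5 | either | yes | 2 | none | Hy's | none | Hy's |
| **Uncovered, of 24** | | | | **5** | **3** | **2** | **0** |

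In R1, 4 of the 5 uncovered patterns have another etiology and 1 is unexplained. In R2 the split is 2 and 1. In R3 both have another etiology.

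**Overlap with Section 7.5.** Of the 5 in R1, 3 meet its bilirubin/INR rule outright: the two at 2.5×ULN, and the one at 1.6×ULN with INR >1.5. The other 2 (1.6×ULN, INR ≤1.5) reach 7.5 only through >8×ULN, persistence beyond 2 weeks or investigator judgment. The corresponding counts are 1 of 3 in R2 and 2 of 2 in R3.

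**Candidate corrections.** If the >5×ULN criterion takes every case not meeting the Hy's Law criterion, each case above 5×ULN meets one or the other, so 0 of 24 are uncovered in all four readings. Deleting the bilirubin condition makes the >5×ULN criterion true for all 24, again 0 uncovered. Only defining an increase as >2×ULN turns R1 into R3 and leaves 2 uncovered.

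**The case against.** The strongest reply is that the firm part of the gap contains only explained cases, which the protocol excludes on purpose both in the Hy's Law bullet and in Section 10.2.3. The next bullet attaches >2×ULN to a bilirubin increase, so that cut-off is a fair reading of the >5×ULN criterion too. The unexplained pattern then disappears, and the 2 remaining patterns are one clinical picture at two INR levels. Until an explanation is found, a single subject with bilirubin >2×ULN meets the Hy's Law criterion alone. For the gap to matter, two of 16 screened healthy subjects would have to show explained, symptom-free elevations of this kind. Section 7.5 would stop both, exclusion 23 (ALT/AST >1.5×ULN) applies at Period 2 Check-in, and the risk/benefit criterion and SAE judgment remain.

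Most of this stands as an argument about probability and impact. It does not rescue the wording. Deliberate exclusion of explained cases does not account for a >5×ULN criterion that counts them while bilirubin is normal and drops them once it rises. The >2×ULN cut-off is plausible but is not stated in that criterion. The other safeguards act on the individual subject or depend on judgment: Section 10.2.3 does not make these cases automatic SAEs, and the asterisk note is permissive and does not alter which cases count.

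**Conclusion.** The concern holds. On the natural reading of the Hy's Law bullet, a symptom-free case with ALT/AST >5×ULN, bilirubin >2×ULN and another etiology counts toward none of the three numeric transaminase criteria, although it would count with normal bilirubin. Symptom-free here also means no fever, rash or eosinophilia >5%, and to count means to supply one of the two subjects needed.

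On that reading the gap is 2 of 24 patterns if an increase is >2×ULN and 5 of 24 if it is any value above ULN. It closes only if the cut-off is >2×ULN and the etiology qualifier governs the INR limb alone. The counts weight all patterns equally and say nothing about how often they occur.

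The event is improbable and the practical impact low. The point is still worth correcting, because the rule is mandatory, ranks severity the wrong way round and contains an undefined term.

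**What to change.** Reword the >5×ULN criterion in 6.3.1 so that it applies when *at least two subjects have ALT or AST >5×ULN and do not meet the Hy's Law criterion below*. Alternatively, delete its bilirubin condition. A cut-off alone is not sufficient on the natural reading.

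The cost is one clause in a protocol amendment. No new tests are needed, since ALT, AST, total bilirubin and INR are already in Table 9.a. The downside is that slightly more cases, some with another explanation, could count toward a pause. If the sponsor intends explained cases not to count, it should say so in the >5×ULN criterion as well, so that etiology is treated alike at every bilirubin level; the bilirubin condition would still need one of the two changes above to cover the unexplained pattern.

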6.3.2 Criteria for Premature Termination or Suspension of Investigational Sites

A study site may be terminated prematurely or suspended if the site (including the investigator) is found in significant violation of GCP, protocol, or contractual agreement, is unable to ensure adequate performance of the study, or as otherwise permitted by the contractual agreement.

6.3.3 Procedures for Premature Termination or Suspension of the Study or the Participation of Investigational Site

In the event that the sponsor, an institutional review board (IRB), or regulatory authority elects to terminate or suspend the study or the participation of a study site, a study-specific procedure for early termination or suspension will be provided by the sponsor; the procedure will be followed by applicable study sites during the course of termination or study suspension.

7.0 SELECTION AND DISCONTINUATION/WITHDRAWAL OF SUBJECTS

All entry criteria, including test results, need to be confirmed prior to randomization.

7.1 Inclusion Criteria

Subject eligibility is determined according to the following criteria prior to entry into the study:

1. In the opinion of the investigator, the subject is capable of understanding and complying with protocol requirements.
2. The subject signs and dates a written, informed consent form and any required privacy authorization prior to the initiation of any study procedures including requesting that a subject fast for any laboratory evaluations.
3. The subject is a healthy adult male or healthy adult female of nonchildbearing potential.
4. The subject is aged 18 to 55 years, inclusive, at the time of informed consent and first study drug dose.
5. The subject weighs ≥ 45 kg and has a body mass index (BMI) between 18.0 and 30.0 kg/m², inclusive at Screening.
6. A male subject who is nonsterilized* and sexually active with a female partner of childbearing potential* agrees to use barrier method of contraception (eg, condom with spermicidal cream or jelly)* from signing of informed consent throughout the duration of the study and for 95 days after last dose. The female partner of a male subject should also be advised to use a highly effective method of contraception.*

* Definitions and highly effective methods of contraception are defined in Section 9.1.9 and reporting responsibilities are defined in Section 9.1.10.

7.2 Exclusion Criteria

Any subject who meets any of the following criteria will not qualify for entry into the study:

1. The subject has received any investigational compound within 30 days prior to randomization.
2. The subject has received TAK-831 in a previous clinical study.
3. The subject is an immediate family member, study site employee, or is in a dependent relationship with a study site employee who is involved in the conduct of this study (eg, spouse, parent, child, sibling) or may consent under duress.
4. The subject has uncontrolled, clinically significant neurologic (including seizure disorders), cardiovascular, pulmonary, hepatic, renal, metabolic, gastrointestinal, urologic, immunologic, or endocrine disease, psychiatric disorder, or other abnormality, which may impact the ability of the subject to participate or potentially confound the study results. It is the responsibility of the investigator to assess the clinical significance; however, consultation with the Medical Monitor may be warranted. There is any finding in the subject's medical history, physical examination, or safety laboratory tests giving reasonable suspicion of a disease that would

contraindicate taking TAK-831, or a similar drug in the same class, or that might interfere with the conduct of the study.

5. The subject has evidence of current cardiovascular, CNS, hepatic, hematopoietic, renal, metabolic, or endocrine dysfunction, serious allergy, asthma, hypoxemia, hypertension, seizures, or allergic skin rash.
6. The subject has current or recent (within 6 months) gastrointestinal disease that would be expected to influence the absorption of drugs (ie, a history of malabsorption, esophageal reflux, peptic ulcer disease, erosive esophagitis, frequent [more than once per week] occurrence of heartburn, or any surgical intervention).
7. The subject has a lifetime history of suicidal ideation as evidenced by a score ≥ 3 in the Columbia-Suicide Severity Rating Scale (C-SSRS) at Screening or Baseline, or a history of suicidal behavior.
8. The subject has a history of cancer, except basal cell carcinoma or in situ cervical cancer that has been in remission for ≥ 5 years prior to first dose of study drug.
9. The subject has a known hypersensitivity to any component of the formulation of TAK-831 or Ensure Plus.
10. If female, the subject is of childbearing potential (eg, premenopausal, not sterilized).
11. If male, the subject intends to donate sperm during the course of this study or for 95 days after the last dose of study drug.
12. The subject has a positive urine drug result for drugs of abuse (defined as any illicit drug use) at Screening or Check-in (Day -1) of Period 1 or 2.
13. The subject has a history of drug abuse (defined as any illicit drug use) or a history of alcohol abuse (defined as regular consumption of 3 or more units per day on 1 occasion per week or 7 or more units in any given week) within 1 year prior to Screening or is unwilling to agree to abstain from alcohol and drugs throughout the study. One unit is equivalent to a half-pint of beer or 1 single measure of spirits or 1 small glass of wine.
14. The subject has taken any excluded medications, supplements, or dietary products during the time periods listed in [Table 7.a](#).
15. The subject has a positive test result for hepatitis B surface antigen (HBsAg), hepatitis C virus (HCV) antibody, or human immunodeficiency virus (HIV) antibody/antigen at Screening or a known history of HIV infection.
16. The subject has used nicotine-containing products (including but not limited to cigarettes, pipes, cigars, chewing tobacco, nicotine patch, or nicotine gum) within 28 days prior to Check-in (Day -1) of Period 1. Cotinine test is positive at Screening or Check-in (Day -1) of Period 1 or 2.
17. The subject has poor peripheral venous access.

18. The subject has donated or lost 450 mL or more of his or her blood volume (including plasmapheresis), or had a transfusion of any blood product within 45 days prior to first dose of study drug.
19. The subject has an abnormal (clinically significant) ECG at Screening or Check-in (Day -1) of Period 1 or 2. Entry of any subject with an abnormal (not clinically significant) ECG must be approved and documented by signature by the principal investigator or designee.
20. The subject has a QT interval with Fridericia correction method (QTcF) >450 msec (males) or >470 msec (females) or PR interval outside the range of 120 to 220 msec, confirmed with 1 repeat testing, at Screening or Check-in (Day -1) of Period 1 or 2.
21. The subject has a supine blood pressure outside of the range of 90 to 140 mm Hg for systolic and 50 to 90 mm Hg for diastolic, confirmed on repeat testing within a maximum of 30 minutes, at Screening or Check-in (Day -1) of Period 1 or 2.
22. The subject has a resting heart rate outside of the range of 40 to 100 beats per minute, confirmed on repeat testing within a maximum of 30 minutes, at Screening Visit or Check-in (Day -1) of Period 1 or 2.
23. The subject has abnormal clinical laboratory test values that suggest a clinically significant underlying disease or has ALT and/or AST >1.5×ULN at Screening or Check-in (Day -1) of Period 1 or 2.
24. The subject has any dietary restrictions or preferences that may interfere with the conduct of the study.

